## **5.2 Selection of Study Population**

The study population in Part 1 consists of HCV genotype 1-infected pediatric subjects without cirrhosis who are naïve to HCV treatment. The study population in Part 2 consists of HCV genotype 1- or 4-infected pediatric subjects with or without compensated cirrhosis, who are treatment-naïve or IFN (IFN or pegIFN with or without RBV) treatment-experienced.

Subjects who meet the inclusion criteria and who do not meet any of the exclusion criteria will be eligible for enrollment into the study.

### **5.2.1 Inclusion Criteria**

1. Male or female  $\geq 3$  to 17 years of age with weight  $\geq 15$  kg at time of enrollment.
2. Willingness to participate in the study for up to 42 months.
3. If female, subject must either be pre-menarche and not sexually active, permanently surgically sterile (bilateral oophorectomy, bilateral salpingectomy or hysterectomy) OR for Women of Childbearing Potential (WOCBP) practicing at least one protocol specified method of birth control (Section 5.2.4), starting at Study Day 1 (or earlier) through at least 30 days after stopping study drug (if not receiving RBV), or for up to 6 months after stopping study drug if receiving RBV (or as directed by local RBV label).
4. If male subject and sexually active with female partner(s) of childbearing potential, subject must agree to practice the protocol specified contraception (Section 5.2.4), from Study Day 1 and for up to 9 months after stopping study drug (or as directed

by the local RBV label if receiving RBV) or from Study Day 1 through 30 days after last dose of study drug for subjects whose study regimen does not include RBV.

5. HCV infection demonstrated by positive anti-HCV Ab and HCV RNA  $\geq 1000$  IU/mL at the time of screening.
6. Screening laboratory results indicating HCV genotype 1 for enrollment into Part 1 and genotype 1 or 4 for enrollment into Part 2.
7. Subject has never received antiviral treatment (including IFN or pegIFN with or without RBV) for hepatitis C infection (treatment-naïve subjects) for Part 1 or Part 2, or subject must have completed their IFN based (IFN or pegIFN with or without RBV only) hepatitis C treatment at least 6 months prior to enrollment into Part 2.
8. Parent or legal guardian with the willingness and ability to provide written informed consent and subject willing and able to give assent, as appropriate for age and country.
9. Females of childbearing potential must have a negative serum pregnancy test result at Screening, and a negative urine pregnancy test at Study Day 1. Females of non-childbearing potential (as defined above) at Screening do not require pregnancy testing.

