  - Hemoglobin < 10 g/dL
  - Platelets < 25,000 cells per mm^3
  - Total bilirubin > 3.0 mg/dL

9. Any current or past clinical evidence of Child-Pugh B or C Classification (Child-Pugh Score  $\geq 7$ ) or clinical history of liver decompensation such as ascites (noted on physical exam), variceal bleeding or hepatic encephalopathy.
10. Confirmed presence of hepatocellular carcinoma indicated on imaging techniques such as computed tomography (CT) scan or magnetic resonance imaging (MRI) within 3 months prior to Screening or on an ultrasound performed at Screening for subjects with cirrhosis (a positive ultrasound result will be confirmed with CT scan or MRI).
11. Male subject who is considering fathering a child or donating sperm during the study or for approximately 120 days after stopping study drug if receiving DAAs only, or for up to 9 months after stopping study drug if receiving RBV (or as directed by local RBV label).

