#### **5.2.4 Contraception Recommendations and Pregnancy Testing**

The contraception recommendations in this paragraph are summarized in relation to the potential risk of the investigational products used in this study. All female subjects who are experiencing menses or are nearing sexual maturation in the opinion of the Principal Investigator, or who are of child-bearing potential should undergo pregnancy testing according to Section 5.3.1.1.

If female, subject must be:

- Pre-menarche and not sexually active, or
- Permanently surgically sterile (bilateral oophorectomy, bilateral salpingectomy or hysterectomy), or
- Practicing at least one of the following methods of birth control, on Study Day 1 (or earlier) through at least 30 days after stopping study drug (if not receiving RBV), or for up to 6 months after stopping study drug if receiving RBV (or as directed by local RBV label).
  - Progestogen-only hormonal contraception (injectable or implantable) associated with inhibition of ovulation, initiated at least 1 month prior to Study Day 1.
  - Bilateral tubal occlusion/ligation.
  - Vasectomized partner(s), provided the vasectomized partner has received medical assessment of the surgical success and is the sole sexual partner of the WOCBP trial participant.
  - Intrauterine device (IUD).
  - Intrauterine hormone-releasing system (IUS).
  - True abstinence: Refraining from heterosexual intercourse when this is in line with the preferred and usual lifestyle of the subject (periodic abstinence [e.g., calendar, ovulation, symptothermal, post-ovulation methods] and withdrawal are not acceptable).

Listed methods of contraception achieve a failure rate of less than 1% per year when used perfectly (consistently and correctly). For oral hormonal contraceptives, failure rates can increase up to 9% with typical use (including inconsistent or incorrect use).

Note: Contraceptive methods with low user dependency are implantable progesterone only hormonal contraception, IUD, IUS, bilateral tubal occlusion, and vasectomized partner.

If required per local practices, male or female condom with or without spermicide OR cap, diaphragm or sponge with spermicide should be used in addition to one of the birth control methods listed above (excluding true abstinence).

If male, subjects must be

- Prepubertal and not sexually active, or
- surgically sterile (vasectomy with medical assessment confirming surgical success), or

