- have a female partner who is postmenopausal or permanently sterile (bilateral oophorectomy, bilateral salpingectomy or hysterectomy), or
- if sexually active with female partner(s) of childbearing potential must agree to practice contraception with a method listed below from Study Day 1 and for up to 9 months after stopping study drug (or as directed by the local RBV label if receiving RBV) or from Study Day 1 and continue for 120 days after last dose of study drug for subjects whose study regimen does not include RBV.
- Condom use in combination with one additional birth control method.
- True abstinence: Refraining from heterosexual intercourse – when this is in line with the preferred and usual lifestyle of the subject. (Note: Periodic abstinence [e.g., calendar, ovulation, symptothermal, post-ovulation methods] and withdrawal are not acceptable).

Additionally, male subjects must agree not to donate sperm from Study Day 1 through 120 days after the end of treatment if taking DAAs only, or for 9 months after the last dose of RBV (or per local RBV label).

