### **Pregnancy Test**

Females of non-childbearing potential (either pre-menarche and not sexually active or permanently surgically sterile as defined above in [Section 5.2.4](#)) at Screening do not require pregnancy testing. All female subjects who are experiencing menses or are nearing sexual maturation in the opinion of the Principal Investigator, or who are of child-bearing potential:

- A serum pregnancy test will be performed at the Screening visit only and analyzed by the central laboratory.
- Pregnancy testing will be performed as specified in [Appendix C](#) regardless of treatment regimen.
- Subjects that receive a RBV containing regimen will have pregnancy tests performed monthly throughout the Treatment Period and through Post-Treatment Week 16 or 4 months after the discontinuation of RBV, or according to the local RBV label and/or local treatment guidelines for RBV.
- Subjects receiving DAAs only should have urine pregnancy testing done through Post-Treatment Week 4.
- Urine pregnancy testing will be performed on-site during the study visit if there is a scheduled visit. The pregnancy result will be captured in the source document and recorded in the eCRF by site personnel. If there is not a scheduled study visit, subjects may either have pregnancy testing performed at the site as an unscheduled study visit or a urine pregnancy test may be conducted by the subject at home with a pregnancy test kit provided by the

site. If a urine pregnancy test is performed at home, site personnel should contact these female study subjects to capture the results of any study-related pregnancy tests in the source records only.

- If a urine pregnancy result is positive, a confirmatory hCG serum test should be collected and sent to the central lab.

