#### **6.1.6 Pregnancy**

Subjects and their partners should avoid pregnancy and males should avoid sperm donation throughout the course of the study, which is defined as from Study Day 1 until 30 days after the last dose of study drug if subjects do not take RBV, or from Study Day 1 until 6 months for WOCBP and 9 months for males after the last dose of the study drug containing RBV (or per local RBV label).

Pregnancy in a study subject must be reported to the AbbVie within 1 working day of the site becoming aware of the pregnancy. Subjects who report a positive pregnancy test during the Treatment Period must be notified to stop RBV (if applicable) immediately. Administration of DAAs may be continued at the investigator's discretion after discussion with the subject, if the benefit of continuing therapy is felt to outweigh the potential risk (as allowed per local guidance) (Section 5.4.1).

Information regarding a pregnancy occurrence in a study subject and the outcome of the pregnancy will be collected for pregnancies occurring up to 30 days after the end of treatment with DAAs only, or through Post-Treatment Week 28 (or per local RBV label) after the last dose of RBV for treatment with DAAs plus RBV. The investigator is encouraged to report the pregnancy information to the voluntary RBV Pregnancy Registry, if RBV is included within the regimen.

Subjects who discontinue study medications due to pregnancy will be monitored for SVR in the Post-Treatment Period as described in Section 5.4.1.

Pregnancy in a study subject is not considered an adverse event. However, the medical outcome of an elective or spontaneous abortion, stillbirth or congenital anomaly is considered a serious adverse event and must be reported to the Sponsor within 24 hours of the site becoming aware of the event.

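### Males on ribavirin-free regimens are given a 30-day post-treatment contraception and sperm-donation period in two protocol sections and 120 days in two others

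*Protocol*

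**What the plan says.** Four sections of the current protocol set a post-treatment period for males on a regimen without RBV.

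- **Section 5.2.1, inclusion criterion 4** (contraception for males sexually active with female partners of childbearing potential): "from Study Day 1 through 30 days after last dose of study drug for subjects whose study regimen does not include RBV". The criterion refers to Section 5.2.4 for the contraception itself.
- **Section 6.1.6** (subjects and partners avoiding pregnancy, males avoiding sperm donation): "from Study Day 1 until 30 days after the last dose of study drug if subjects do not take RBV".
- **Section 5.2.4, contraception**: "from Study Day 1 and continue for 120 days after last dose of study drug for subjects whose study regimen does not include RBV".
- **Sperm donation, also in Section 5.2.4**: "male subjects must agree not to donate sperm from Study Day 1 through 120 days after the end of treatment if taking DAAs only".
- **Section 5.2.2, exclusion criterion 11**, which excludes a male "considering fathering a child or donating sperm during the study or for approximately 120 days after stopping study drug if receiving DAAs only".

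The RBV-free regimen is a real arm of the plan: Tables 5 and 6 assign it to genotype 1b subjects.

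**The concern.** The same subjects on the same regimen, counted from the same starting point, are given two different durations. Criterion 4 is an eligibility condition that depends on the subject's agreement, so the protocol should say unambiguously what he agrees to. As written, it gives one figure and points to a section that gives another.

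Two sites could therefore counsel adolescent males differently on a reproductive-safety rule. They could also judge the same behaviour differently, as compliance at one site and as a protocol deviation at the other. The statistical results are not at risk: no efficacy endpoint, analysis or sample size depends on this period.

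**Working it through.** There is no power or sample-size figure to reproduce. The check is a side-by-side reading of the current text.

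**Step 1. Stated periods after the last dose, by sex and regimen**

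| Protocol section | Topic | Male, no RBV | Male, RBV | Female, no RBV | Female, RBV |
|---|---|---|---|---|---|
| 5.2.1, criteria 3 and 4 | contraception | **30 days** | 9 months | 30 days | 6 months |
| 5.2.2, criteria 1 and 11 | pregnancy, fathering, sperm donation | **120 days** | 9 months | 30 days | 6 months |
| 5.2.4 | contraception | **120 days** | 9 months | 30 days | 6 months |
| 5.2.4 | sperm donation | **120 days** | 9 months | not applicable | not applicable |
| 6.1.6 | pregnancy, sperm donation | **30 days** | 9 months | 30 days | 6 months |

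Three of the four sex-by-regimen columns carry one number throughout. For example, Section 6.1.6 gives the RBV periods as "until 6 months for WOCBP and 9 months for males after the last dose of the study drug containing RBV", which matches the other sections. Qualifiers differ from place to place (minimum, maximum, approximate), but the numbers agree. Only the column for males without RBV contains two numbers.

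**Step 2. Does each topic conflict on its own?**

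- Contraception: 30 days in 5.2.1 against 120 days in 5.2.4.
- Sperm donation: 30 days in 6.1.6 against 120 days in 5.2.2 and 5.2.4.

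Both do, so the split cannot be explained by one figure belonging to contraception and the other to sperm donation.

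**Step 3. Size of the gap**

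- Difference: 120 − 30 = 90 days, that is, day 31 to day 120 after the last dose.
- Ratio: 120 / 30 = 4.

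In that window a sexually active male who uses no contraception, and whose partner could become pregnant, complies with criterion 4 and breaches Section 5.2.4. A male who donates sperm complies with Section 6.1.6 and breaches Section 5.2.4.

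**Step 4. Can the text resolve it?**

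- The deferrals to a local label in these passages attach to RBV, so they do not reach the RBV-free period.
- The male 30 days is not framed as a minimum. The female RBV-free period in Section 5.2.4 is: "through at least 30 days after stopping study drug (if not receiving RBV".
- Section 6.1.6 presents its 30 days as the definition of the period, not as an example.
- No passage says that one section takes precedence.

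**Step 5. Is it superseded text?** No. The new-wording entries in Appendix F for these statements repeat the same 30-day and 120-day values. This amendment changed the male RBV period from 7 to 9 months in all of these places and left the RBV-free period split. Section 1.1 lists the correction of inconsistencies among the amendment's purposes.

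**Step 6. How many subjects?** The documents do not give the number of males on RBV-free treatment. A planned ceiling for adolescents can be built. All genotype 4 subjects receive RBV, which leaves about 12 genotype 1 subjects aged 12 to 17 in Part 1 and about 16 in Part 2: 12 + 16 = 28 of about 62. That is before restricting to males, to genotype 1b and, for contraception, to those sexually active with partners of childbearing potential. It assumes that the remaining planned Part 1 subjects, aged 3 to 11, are largely outside the practical reach of the rule; Section 5.2.4 accepts prepubertal males who are not sexually active without contraception.

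**The case against.** The conflict itself is hard to dispute. The case on the other side concerns its weight.

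- **The protocol can be followed.** A male who observes 120 days satisfies every section. This stands.
- **Eligibility screening already uses the longer figure.** Under Section 5.2 a subject must meet all inclusion criteria and no exclusion criteria, so a site reads criteria 4 and 11 together. This stands for fathering and sperm donation at enrollment. It does not settle contraception: a male with no plan to father a child within 120 days passes criterion 11 and can still agree, under criterion 4, to only 30 days of contraception. Nor does it settle the post-treatment instruction in Section 6.1.6.
- **Criterion 4 points to Section 5.2.4, the more detailed section.** That makes it less likely that a site misses the longer figure. It does not establish precedence, and the reader who follows the pointer meets the contradiction.
- **Few subjects are affected.** This is probably true: the ceiling of about 28 shrinks at each restriction. It limits the consequences without making the text consistent.
- **What subjects were told cannot be assessed**, because the consent pages are not available for review. This also stands.

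One neighbouring difference is not part of this point. Default pregnancy testing after RBV runs "through Post-Treatment Week 16 or 4 months after the discontinuation of RBV, or according to the local RBV label", which is shorter than the female contraception period of up to 6 months. These are separate requirements, both defer to the local label, and they can be followed together.

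**Conclusion.** The concern holds. For males on RBV-free regimens the current protocol states 30 days in Sections 5.2.1 and 6.1.6, and 120 days in Sections 5.2.2 and 5.2.4. It is an internal inconsistency in an eligibility and reproductive-safety rule, and it should be fixed. Its pattern, one inconsistent cell among four, suggests an oversight; nothing in the documents presents it as deliberate.

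The conclusion rests on the text alone. The only assumptions concern reach: that the planned enrollment numbers are met, and that the rule matters in practice mainly for adolescents. Neither affects whether the passages conflict.

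**What to change.** Reconcile the five statements: Section 5.2.1 criterion 4, Section 5.2.2 criterion 11, both male statements in Section 5.2.4 (contraception and sperm donation), and Section 6.1.6. One RBV-free male duration should be stated identically in each. Section 6.1.6 currently gives one RBV-free period for all subjects, so it may need separate male and female wording if the two are meant to differ. Which figure applies is for the sponsor to decide; this review takes no position.

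The cost is wording in four protocol sections and in any subject-facing text that repeats the figure. No visits, procedures or analyses change.

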#### **Rationale for Inclusion Criteria**

- |             |  |
|-------------|--|
| 1, 2, 5 – 7 | To select the appropriate subject population with sufficient disease severity for evaluation |
| 3, 4, 9     | RBV has known teratogenic effects  |
| 8           | In accordance with harmonized Good Clinical Practice (GCP)                                   |

#### **5.2.2 Exclusion Criteria**

A subject will be excluded from the study if he/she meets any of the following criteria:

1. Female subject who is pregnant, breastfeeding or is considering becoming pregnant during the study or for approximately 30 days after stopping study drug (if not receiving RBV), or for up to 6 months after stopping study drug if receiving RBV (or as directed by local RBV label).
2. Use of known strong inducers and inhibitors (e.g., gemfibrozil) of cytochrome P450 2C8 (CYP2C8) in subjects receiving dasabuvir, or strong or moderate inducers of CYP3A, medications listed below, or medications contraindicated for ritonavir or RBV (for those that receive RBV), within 2 weeks or 10 half-lives, whichever is longer, of the respective medication prior to study drug administration including but not limited to:

**Table 7. Medications Contraindicated for Use with the Study Drug Regimen**

Alfuzosin	Ethinyl estradiol-containing medications	Pimozide
Astemizole	Fusidic Acid	Ranolazine
Atorvastatin	Gemfibrozil a	Rifampin
Blonanserin	Lovastatin	Salmeterol
Carbamazepine	Lurasidone	Sildenafil b
Cisapride	Methylergonovine	Simvastatin
Colchicine c	Midazolam (oral)	St. John's Wort
Dihydroergotamine	Phenobarbital	Terfenadine
Dronedarone	Phenytoin	Triazolam
Efavirenz		
Ergotamine		
Ergonovine		

- a. Strong CYP2C8 inhibitors (e.g., gemfibrozil) and CYP2C8 inducers are not contraindicated with ombitasvir, paritaprevir and ritonavir (for GT4 subjects).
- b. When used for the treatment of pulmonary arterial hypertension.
- c. When used in patients with renal or hepatic impairment.

Note: Not all medications contraindicated with ribavirin are listed above. Refer to the most current package inserts or product labeling of ribavirin for a complete list of contraindicated medications.

For medications contraindicated with AbbVie's 2D and 3D regimen, refer to the recommended prescribing information section of the approved local product labels in countries where the regimen contained in this study (i.e., ombitasvir/paritaprevir/ritonavir with or without dasabuvir) has received marketing authorization. If locally approved labels are not available, refer to the following Contraindicated Medication list:

3. Clinically significant abnormalities or co-morbidities, other than HCV infection that make the subject an unsuitable candidate for this study or treatment with RBV (if applicable) in the opinion of the investigator.
4. Positive test result for Hepatitis B surface antigen (HbsAg) or anti-HIV antibody (HIV Ab) test.
5. Current enrollment in another interventional clinical study, previous enrollment in this study, prior or current use of any investigational or commercially available anti-HCV agents other than IFNs or RBV or receipt of any investigational product within 6 weeks prior to study drug administration.
6. History of solid organ transplant.
7. Prior or current use of any investigational or commercially available anti-HCV agents other than IFN, pegIFN or RBV, including telaprevir, boceprevir, sofosbuvir, ombitasvir, dasabuvir, paritaprevir, ledipasvir, daclatasvir, simeprevir, elbasvir, grazoprevir or an investigational DAA.
8. Screening laboratory analyses showing any of the following abnormal laboratory results:
  - Albumin < 2.8 g/dL
  - Hemoglobin < 10 g/dL
  - Platelets < 25,000 cells per mm^3
  - Total bilirubin > 3.0 mg/dL

9. Any current or past clinical evidence of Child-Pugh B or C Classification (Child-Pugh Score  $\geq 7$ ) or clinical history of liver decompensation such as ascites (noted on physical exam), variceal bleeding or hepatic encephalopathy.
10. Confirmed presence of hepatocellular carcinoma indicated on imaging techniques such as computed tomography (CT) scan or magnetic resonance imaging (MRI) within 3 months prior to Screening or on an ultrasound performed at Screening for subjects with cirrhosis (a positive ultrasound result will be confirmed with CT scan or MRI).
11. Male subject who is considering fathering a child or donating sperm during the study or for approximately 120 days after stopping study drug if receiving DAAs only, or for up to 9 months after stopping study drug if receiving RBV (or as directed by local RBV label).

#### **Rationale for Exclusion Criteria**

- |                    |   |
|--------------------|---|
| 1, 3, 7, 8, 10, 11 | To ensure safety of the subjects throughout the study   |
| 2                  | To avoid bias for the evaluation of efficacy and safety by concomitant use of other medications |
| 4 – 6, 9           | To avoid bias for the evaluation of efficacy and safety   |

